6.6.2. Vital Signs

Vital signs data includes weight, pulse, systolic blood pressure, and diastolic blood pressure. Vital sign summaries will include all vital sign assessments from the on-treatment period. All vital sign assessments will be listed, and those collected outside the on-treatment period will be flagged in the listing. Measurements were only to be provided once per timepoint. If multiple assessments are provided per timepoint, the maximum value will be used for reporting.

Vital signs data will be summarized using simple descriptive statistics (mean, Std Dev, median, quartiles, minimum, and maximum) of actual values and change from baseline for each nominal visit over time (i.e. unscheduled assessments will be excluded). The total number of participants for change from baseline will include all participants who have both a baseline value and a value at the nominal visit. Baseline will be selected as defined in Section 3.4.

The number and percent of participants in each of the following minimum and maximum blood pressure, body weight, and pulse categories will be presented:

- Increase in Systolic Blood Pressure ≥40 mmHg
- Decrease in Systolic Blood Pressure ≥ 40 mmHg
- Increase in Diastolic Blood Pressure ≥20 mmHg
- Decrease in Diastolic Blood Pressure ≥20 mmHg
- Increase in Diastolic Blood Pressure ≥60 mmHg
- Maximum Pulse Rate > 120 bpm
- Minimum Pulse Rate < 50 bpm
- Maximum increase in pulse rate ≥ 30 bpm
- Maximum decrease in pulse rate ≥ 30 bpm
- Decrease in Body Weight ≥ 10%
- Increase in Body Weight between 10% and 20%
- Increase in Body Weight $\geq 20\%$

All assessments, including unscheduled assessments will be considered. A participant can be included in multiple categories if different criteria are met at different timepoints.

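### SAP 6.6.2 keeps the highest of several vital-sign readings at a timepoint; taken literally, this can only lower the section's own minimum and decrease counts

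*SAP*

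**What the plan says.** SAP 6.6.2 names four parameters: "Vital signs data includes weight, pulse, systolic blood pressure, and diastolic blood pressure". It expects a single reading each time ("Measurements were only to be provided once per timepoint") and then gives one rule for the exception: "If multiple assessments are provided per timepoint, the maximum value will be used for reporting". The rule is not limited to any parameter or direction.

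The section plans two kinds of summary:

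- **By-visit descriptive statistics** of values and changes from baseline at nominal visits, leaving out unscheduled readings.
- **A category table**, introduced by: "The number and percent of participants in each of the following minimum and maximum blood pressure, body weight, and pulse categories will be presented". Five of its rows look downward: "Minimum Pulse Rate < 50 bpm", "Maximum decrease in pulse rate ≥ 30 bpm", "Decrease in Systolic Blood Pressure ≥ 40 mmHg", a diastolic fall of at least 20 mmHg, and a weight loss of at least 10%.

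After the list comes: "All assessments, including unscheduled assessments will be considered". The next sentence lets a participant fall into several categories when the criteria are met at different timepoints. The section also has every vital-sign reading listed. SAP 5.2.10 brings unscheduled readings into the worst on-treatment value for vital signs. SAP 3.4 defines the safety baseline as the last assessment up to and including the day of first dose.

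**The concern.** The highest reading is the worst case only for increases. For the five downward rows it is the most favourable reading of the set. A programmer who follows the duplicate rule as written therefore feeds the least abnormal value into the rows meant to find low values. The by-visit statistics are affected too, because a visit with duplicates always contributes its highest reading.

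Safety and tolerability are this study's primary objective, so these tables should carry no built-in direction. The pulse row matters somewhat more than the others because it is the only planned count of low heart rate. SAP 6.6.3 gives ECG heart rate descriptive statistics only, and its categories cover QTc, QRS and PR. In the Schedule of Activities, planned ECGs run each cycle up to Cycle 5 and then at end of treatment, while vital signs continue every cycle.

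**Working it through.** The plan states no figure to reproduce on this point. The check applies the thresholds of SAP 6.6.2 to assumed readings. All readings below are illustrations, not data.

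**Step 1: one pair of on-treatment readings per downward category.** Fall = baseline − retained reading; for weight, 100 × (baseline − retained reading) / baseline.

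| Category | Assumed baseline | Assumed pair | Highest kept (rule as written) | Lowest kept |
|---|---|---|---|---|
| Pulse < 50 bpm | not used | 46, 58 | 58: not counted | 46: counted |
| Pulse fall ≥ 30 bpm | 80 | 46, 58 | 80 − 58 = 22: not counted | 80 − 46 = 34: counted |
| Systolic fall ≥ 40 mmHg | 140 | 96, 108 | 140 − 108 = 32: not counted | 140 − 96 = 44: counted |
| Diastolic fall ≥ 20 mmHg | 85 | 62, 70 | 85 − 70 = 15: not counted | 85 − 62 = 23: counted |
| Weight loss ≥ 10% | 70.0 kg | 62.5, 63.5 kg | 100 × 6.5/70.0 = 9.3%: not counted | 100 × 7.5/70.0 = 10.7%: counted |

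**Step 2: direction.** For a fixed baseline, if the highest on-treatment reading meets a downward criterion, the lowest meets it too. The reverse does not hold. So the rule can remove participants from these rows but cannot add any.

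**Step 3: how much one duplicated timepoint could lose.** Suppose two independent readings each fall below the threshold with assumed probability p. Keeping the highest flags the timepoint with probability p²; counting any low reading flags it with probability 1 − (1 − p)².

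| p (assumed) | Highest kept | Any low reading counts |
|---|---|---|
| 0.05 | 0.0025 | 0.0975 |
| 0.10 | 0.01 | 0.19 |
| 0.20 | 0.04 | 0.36 |
| 0.50 | 0.25 | 0.75 |

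Independence is the pessimistic end of this range. If the two readings are identical, nothing is lost.

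**Step 4: effect on the tables.** With 100 treated participants, one participant missed lowers a percentage by 1/100 = 1 point, and only if no other reading of that participant on treatment meets the criterion. For a by-visit mean, take the systolic pair 96 and 108: the pair's mean is 102 and the reported value is 108, a difference of 6 mmHg. One such participant among 100 at a visit raises the visit mean by 6/100 = 0.06 mmHg.

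**Step 5: what cannot be computed.** The documents give no frequency of duplicates, so no overall bias can be stated.

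**The case against.** The best counter-argument is that the category table is already safe. It is introduced as covering minimum and maximum categories, and the sentence "All assessments, including unscheduled assessments will be considered" follows it directly and is worded more widely than unscheduled readings alone. The section also says its summaries take in all on-treatment assessments, and SAP 5.2.10 points to a worst case. On this reading the duplicate rule only fixes the single value used by visit. That may well be the intention, and it is why the point is a conflict to resolve and not a proven loss. But the text never says that the lower of two readings at the same timepoint counts. The sentence on different timepoints fits one value per timepoint, and nothing here reaches the by-visit statistics.

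A reader might also infer more than the documents support:

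- **That low readings are deleted.** They are not. Every reading is listed. A low value can also be reported as an adverse event if it meets Protocol 8.5, for instance because of symptoms, further work-up or a dosing change.
- **That AV block could be masked.** AV block and PR prolongation are assessed by ECG, and SAP 6.6.3 tabulates PR separately. The vital-signs rule does not touch these.
- **That repeats are taken mostly after a low first reading.** This is plausible, but no passage says so. Repeats entered as unscheduled visits would enter the category table in their own right.
- **That baseline is a maximum as well.** SAP 6.6.2 refers baseline to Section 3.4, which takes the last assessment. A maximum baseline would in any case work the other way: with assumed baseline systolic readings of 130 and 142 and a later 100, the higher baseline gives a fall of 42 and the lower one 30.

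**Conclusion.** The conflict is real and minor. As written, the duplicate rule is the wrong way round for five categories of the same section and pushes by-visit values upward wherever duplicates exist. The direction for on-treatment duplicates is certain if the rule is applied literally to the category table. If the later sentence is meant to override it there, only the by-visit effect remains. The size is unknown and probably small, since duplicates are the exception. The incidence of adverse events, which is the primary endpoint, and the sample size are not affected.

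**What to change.** In SAP 6.6.2, state that the minimum and decrease categories use the lowest on-treatment reading and the maximum and increase categories the highest, taken over all readings including duplicates at the same timepoint. For the by-visit descriptive statistics, replace the maximum with one direction-neutral rule; the mean of the duplicates or the last reading would both serve, and the choice matters less than fixing it in advance. Leave baseline as the last assessment under Section 3.4.

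The cost is one SAP sentence and a small programming change. No new data are needed.

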Unscheduled assessments will be utilized in addition to planned assessments.

Shift tables will be provided for baseline value versus worst on-treatment value.

Additionally maximum increases from baseline (including scheduled and unscheduled assessments) will be summarized based on the following categories:

- Change > 60 msec,
- Change >30 msec but \le 60 msec,
- Change ≤ 30 msec

For QRS maximum increases from baseline, the following categories will be applied:

- QRS change \geq 50% if absolute baseline value was <100 msec,
- QRS change \geq 25% if absolute baseline value was \geq 100 msec

For PR interval, the number (%) of subjects with maximum post-dose PR interval values and maximum increases from baseline in the following categories will be tabulated:

Absolute Value (msec)	< 160
	≥160 - < 180
	≥180 - <200
	≥200 - <220
	≥220 - <240
	≥240 – 260
	≥260
Absolute Change (msec)	40 - <60

	≥60 - <80
	≥80
Relative Change from baseline	>25%

6.6.4. Performance Status

ECOG performance status with shift from ECOG=0 or 1 to ECOG 2 or higher will also be presented in a data listing.

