#### Additional Safety Analyses

Other safety parameters, including study treatment exposure, laboratory, electrocardiogram (ECG), vital signs measurements, dose reductions due to AEs, and temporary and permanent discontinuations due to AEs, will be summarized descriptively.

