## 4.1. Inclusion Criteria

Participant eligibility should be reviewed and documented by an appropriate member of the Investigator's study team before participants are included in the study.

Participants must meet all of the following inclusion criteria to be eligible for enrollment into the study:

- 1. Evidence of histologically or cytologically confirmed diagnosis of unresectable advanced and/or recurrent NSCLC that carries an ALK rearrangement, as detected by an appropriate test.
- 2. Disease progression or intolerance to 1 previous treatment with ALK TKI. participants may have also had prior chemotherapy for their advanced and/or recurrent disease.
- 3. Participants with asymptomatic CNS metastases (including participants controlled with stable or decreasing steroid use within the last 2 weeks prior to study enrollment) will be eligible.
- 4. Age  $\geq 18$  years.
- 5. Eastern Cooperative Oncology Group (ECOG) performance status (PS) 0, 1, or 2.
- 6. Adequate hematologic and renal function as defined as:
  - a. Absolute neutrophil count (ANC)  $\geq 1,000/\text{mm}^3$ ;
  - b. Platelets  $\geq$  50,000/mm^3;
  - c. Hemoglobin  $\geq 8 \text{ g/dL}$ ;
  - d. Estimated creatinine clearance  $\geq$ 30 mL/min as calculated using the method standard for the institution.
- 7. Adequate liver function, including:
  - a. Total serum bilirubin  $\leq 1.5 \times$  upper limit of normal (ULN);
  - b. Aspartate aminotransferase (AST) and alanine aminotransferase (ALT)  $\leq 2.5 \times \text{ULN} (\leq 5.0 \times \text{ULN} \text{ in case of liver metastases}).$
- 8. Adequate pancreatic function, including:
  - a. Serum total amylase  $\leq 1.5 \times ULN.*$
  - b. Serum lipase  $<1.5 \times ULN$ .

\*if total amylase >1.5  $\times$  ULN, but pancreatic amylase is within the ULN, the participant may be enrolled.

- 9. Acute effects of any prior therapy resolved to baseline severity or to CTCAE Grade <1 except for AEs that in the Investigator's judgment do not constitute a safety risk for the participant.
- 10. Systemic anticancer therapy completed within a minimum of 5 half-lives of study enrollment (unless clinically meaningful tumor flare per discretion of the Investigator, in which discussion with the Sponsor is warranted).
- 11. Evidence of a personally signed and dated informed consent document indicating that the participant (or a legally acceptable representative) has been informed of all pertinent aspects of the study.

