## 7.2.1. Physical Examination

• Participants will have a physical examination to include major body systems, body weight, blood pressure, pulse rate, and assessment of ECOG performance status at the time points described in the Schedule of Activities. Blood pressure and pulse rate should be taken with the participant in the seated position after the participant has been sitting quietly for at least 5 minutes.

Investigators should pay special attention to clinical signs related to previous serious illnesses.

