#### ECG Findings That Qualify as SAEs

- Change in pattern suggestive of new myocardial infarction.
- Sustained ventricular tachyarrhythmias (>30 seconds' duration).
- Second- or third-degree AV block requiring pacemaker placement.
- Asystolic pauses requiring pacemaker placement.
- Atrial flutter or fibrillation with rapid ventricular response requiring cardioversion.
- Ventricular fibrillation/flutter.
- At the discretion of the Investigator, any arrhythmia classified as an adverse experience.

The enumerated list of major events of potential clinical concern are recommended as "alerts" and not to be considered as all inclusive of what to be reported as AEs/SAEs.

Abbreviations: AE=adverse event; AV=atrioventricular; ECG=electrocardiogram; PVC=premature ventricular complex; QTcF=QT interval calculated using Fridericia's correction factor; SAE=serious adverse event.

Score	Definition
0	Fully active, able to carry on all pre-disease performance without restriction.
1	Restricted in physically strenuous activity but ambulatory and able to carry out work of a light or sedentary nature, eg, light house work or office work.
2	Ambulatory and capable of all self-care but unable to carry out any work activities. Up and about more than 50% of waking hours.
3	Capable of only limited self-care, confined to bed or chair more than 50% of waking hours.
4	Completely disabled. Cannot carry on any self-care. Totally confined to bed or chair.
5	Dead

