3.4. Baseline Variables

Start and end dates of study treatment:

The date of first dose (start date) of study treatment is the earliest date of non-zero dosing of the study drug.

The date of last dose of study treatment is the latest date of non-zero dosing of the study drug.

Definition of baseline:

No windowing will be applied when defining baseline, except as noted in Section 5.2.8 for tumor assessments. Any deviations from the protocol specified window will be documented as protocol deviations. A separate definition of adequate baseline will be provided for tumor assessment related antitumor activity endpoints.

For antitumor activity analyses and baseline characteristics associated with tumor assessments the last assessment prior to treatment start date will serve as the baseline assessment.

For safety (including laboratory, vital signs and Eastern Cooperative Oncology Group (ECOG) performance status) the last assessment performed on or prior to date of the first

dose of study treatment will serve as the baseline assessment. If there are no observations meeting these criteria, then baseline is considered missing.

Participants who start treatment and discontinue from the study on the same day may have two different sets of data collected on study day 1 (one during study and one in the End of Treatment (EOT) visit. Data reported at the EOT visit are not eligible for baseline selection.

Triplicate electrocardiograms (ECGs) are collected pre-dose; therefore, the baseline for each ECG measurement is the average of the latest pre-dose triplicate measurements. Unscheduled assessments will not be included in the calculation of the average.

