6.5. Baseline and Other Summaries and Analyses

6.5.1. Baseline Summaries

• Demographic and Physical Characteristics

The following demographic and baseline characteristics will be summarized by number and percentage:

- o Gender (male, female)
- o Age (18-<45; 45- <65; >65)
- ECOG Performance status

Age (continuous) and weight (kg) will be summarized with descriptive statistics (mean, median, Std Dev, minimum, and maximum, inter quartile range).

Disease Characteristics

The following baseline disease characteristics will be summarized by number and percentage:

Measurable disease at baseline (yes/no) (see Section 5.2.5)
 PFIZER CONFIDENTIAL

^a more than 26 weeks after last adequate tumor assessment.

- o Involved tumor sites at baseline.
- O Number of sites of disease at baseline $(1, 2, \ge 3)$

Involved tumor sites at baseline will be derived from target and non-target lesions at baseline. Each participant will be counted once per organ. Similarly, number of sites of disease at baseline will be derived by counting the number of unique organ sites from target and non-target lesions at baseline. "Other" will be counted as one organ site.

• Medical History

Medical history will be coded using the most current version of MedDRA and summarized by MedDRA's SOC and PT. Each participant will be counted only once within each PT or SOC. Summaries will be ordered by primary SOC and PT in descending order of frequency. Separate summaries will be provided for past and present conditions.

• Prior Anticancer Treatments

Prior anticancer treatments include systemic therapy, radiation, and surgery. The number and percentage of participants in each of the following anticancer therapy categories will be tabulated:

- o Participants with at least one type of prior anticancer treatment;
- o Participants with at least one prior anticancer drug therapy;
- o Participants with at least one prior anticancer radiotherapy;
- o Participants with at least one prior anticancer surgery.

Prior anticancer drug therapy will be summarized as follows based on the number and percentage of participants:

- o Number of prior anticancer therapy regimens: missing $/1/2/3/\ge 4$;
- o Number of participants who received prior chemotherapy
- Number of participants who received 1st generation (Crizotinib) or 2nd generation (Alectinib, Certinib or Brigatinib) ALK Inhibitor (ALKi) as Prior ALKi

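### The only specified post-baseline ECOG output (SAP 6.6.4) cannot pick up worsening to ECOG 3 or 4 in participants who enter at ECOG 2, an eligible group

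*SAP*

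**What the plan says.** **Who can enter.** Protocol 4.1, item 5, requires "Eastern Cooperative Oncology Group (ECOG) performance status (PS) 0, 1, or 2". ECOG 2 is therefore an ordinary eligible grade.

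**What is collected.** Protocol 7.2.1 places ECOG within the physical examination, which covers "weight, blood pressure, pulse rate, and assessment of ECOG performance status at the time points described in the Schedule of Activities". The Schedule of Activities marks ECOG at Screening, Cycle 1 Day 1, Day 1 of every cycle and End of Treatment. The scale in Protocol Appendix 5 continues above 2; grade 3, for example, is "Capable of only limited self-care, confined to bed or chair more than 50% of waking hours".

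**What is defined for analysis.** SAP 3.4 names ECOG among the safety measures that take their baseline from the last assessment on or before first dose.

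**What is reported.** Two ECOG outputs are specified:
- SAP 6.5.1 includes ECOG in the list headed "The following demographic and baseline characteristics will be summarized by number and percentage". This is baseline only.
- SAP 6.6.4 states: "ECOG performance status with shift from ECOG=0 or 1 to ECOG 2 or higher will also be presented in a data listing". This is the whole section.

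**The concern.** The condition in SAP 6.6.4 would suit a trial that enrolled only ECOG 0 or 1, because moving to 2 or higher would then mark a meaningful decline for everyone. This trial also enrols ECOG 2. Those participants already stand at the level the rule treats as the outcome, so they do not qualify for the listing however far they decline directly from entry.

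The primary objective is safety and tolerability. A reader of the listing could take the absence of ECOG 2 entrants to mean that none of them deteriorated, when the rule simply does not look at them. What is at stake is the completeness of one descriptive safety output. No estimate, interval or endpoint depends on it.

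**Working it through.** No sample size, power or error-rate figure bears on this point, and the plan states no figure of its own to reproduce. The check has three parts.

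**1. Which transitions the rule captures.** Inputs: eligible baseline grades 0, 1, 2 (Protocol 4.1); worst on-treatment grade up to 4 (Protocol Appendix 5; grade 5 is death, which SAP 6.1.1.1 tabulates separately); the condition in SAP 6.6.4.

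| Baseline | Possible worsening to | Captured | Missed |
|---|---|---|---|
| 0 | 1, 2, 3, 4 | 2, 3, 4 | 1 |
| 1 | 2, 3, 4 | 2, 3, 4 | none |
| 2 | 3, 4 | none | 3, 4 |

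Total possible: 4 + 3 + 2 = 9. Captured: 3 + 3 + 0 = 6. From baseline 0 or 1 the rule captures 6 of 7; from baseline 2 it captures 0 of 2. The missed step from 0 to 1 appears to be a deliberate threshold. The missed steps from 2 do not follow from any stated reason.

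The sentence does not say that the shift is measured from baseline, but SAP 3.4 defines an ECOG baseline, so that is the natural reading. If it meant visit to visit, a direct move from 2 to 3 or 4 would still fail the condition.

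**2. Whether another specified output fills the gap.**
- SAP 6.5.1: baseline only.
- SAP 6.6.2: "Vital signs data includes weight, pulse, systolic blood pressure, and diastolic blood pressure"; ECOG is not included.
- SAP 6.4: no subset analyses, so nothing is shown by baseline ECOG.
- Protocol Summary, Additional Safety Analyses, and Protocol 9.6: no ECOG analysis is named.
- SAP 6.6.5: physical examination findings are listed, but ECOG is not mentioned there.

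None of these clearly specifies an on-treatment ECOG display.

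**3. How many participants could be affected.** The group left out is the ECOG 2 entrants who worsen, not all ECOG 2 entrants. With N = 100 treated (Protocol 9.2), entry share *s* and probability of worsening *q*:

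number left out = 100 × *s* × *q*

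The documents give neither *s* nor *q*. Assuming *s* = 5-20% and *q* = 10-40%:
- low end: 100 × 0.05 × 0.10 = 0.5
- middle: 100 × 0.10 × 0.20 = 2
- high end: 100 × 0.20 × 0.40 = 8

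**The case against.** The strongest reply is that the ECOG values may be displayed after all. The word *also* in SAP 6.6.4 suggests that the listing accompanies another ECOG presentation. Protocol 7.2.1 puts ECOG inside the physical examination, and SAP 6.6.5 lists physical examination findings without any filter on baseline grade. On that reading every ECOG value might be listed, with 6.6.4 flagging a subset.

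This stands in part. A reader might infer from 6.6.4 that decline in ECOG 2 entrants will never be shown, and the documents do not establish that. But no companion display is specified. Body weight, blood pressure and pulse sit in the same sentence of Protocol 7.2.1 and are analysed under vital signs, and ECOG has its own SAP section, so 6.6.5 cannot be relied on to cover it. A raw listing of findings would also not be a shift display.

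A second reply is that a tolerability signal would not be lost. Protocol 8.3 has worsening signs and symptoms of the malignancy reported as adverse events. SAP 6.1.1.1 tabulates adverse events by maximum grade, seriousness and withdrawal, and deaths, for all treated participants, and SAP 6.6.2 tabulates weight loss of 10% or more. This stands: the clinical events behind a decline may well appear, though not as an ECOG shift.

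Third, the protocol promises no ECOG analysis, so no commitment is broken. That also stands.

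**Conclusion.** The point holds as a minor gap. As written, the only specified post-baseline ECOG output uses a condition that does not fit the eligible population, and worsening from 2 to 3 or 4 is in no clearly specified output although the data are collected at every cycle. That conclusion follows from the text alone.

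The size rests on assumptions: about 0.5 to 8 of 100 participants, if 5-20% enter at ECOG 2 and 10-40% of those worsen.

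Two stronger readings should be resisted. A reader might infer that ECOG 2 entrants are the group most likely to deteriorate; nothing in either document says so. A reader might also take all assumed ECOG 2 entrants, 5 to 20 of 100, as the number affected; that counts people whose status may never worsen. The primary adverse event analysis and all secondary endpoints are untouched.

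**What to change.** In SAP 6.6.4, change the listing condition to any worsening from baseline ECOG, including 2 to 3 or 4. That alone closes the gap and captures all nine transitions.

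Preferably also add a shift table of baseline ECOG (0, 1, 2, missing) by worst on-treatment ECOG (0, 1, 2, 3, 4, missing) in the safety set. This matches the baseline-by-worst displays already planned for laboratory grades (SAP 3.5.3) and QTc (SAP 6.6.3). If *also* refers to an intended companion display, name it in the section; if ECOG is meant to appear in the physical examination listing, say so in 6.6.5.

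The cost is one table or a slightly longer listing, which will now include steps from 0 to 1. No new data or visits are needed. No protocol amendment is needed either: Protocol 9 requires one only for major changes to the primary endpoint or its analysis.
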